8.1. Primary Immunogenicity Analysis

The primary immunogenicity endpoints HAI and Neut seroconversion, percentage of subjects with titer $\geq 1:40$, and GMTs against the homologous A/H7N9 vaccine strain 21 days after the second vaccination will be summarized as described above. Regression modelling of seroconversion and log titers is planned as described in [Section 8.3.2](#).

8.2. Secondary Immunogenicity Analyses

The secondary immunogenicity endpoints HAI and Neut seroconversion, percentage of subjects with titer ≥ 40 , and GMTs against the homologous A/H7N9 vaccine strain 8 and 21 days after the first vaccination and 8 days after the second vaccination will be summarized as described above. No formal hypothesis testing is planned.

8.3. Exploratory Immunogenicity Analyses

Immunogenicity data summaries and analysis for exploratory endpoints will be presented for the PP populations.

8.3.1. Covariate Analysis

As an exploratory analysis, seroconversion and GMT of serum antibody for both HAI and Neut at 21 and 180 days after second vaccination will be summarized by study arm stratified

by age (categorized as those subjects ages 18-34, 35-49, 50-64) in [Table 27](#), [Table 28](#), [Table 29](#), and [Table 30](#), by sex in [Table 31](#), [Table 32](#), [Table 33](#), and [Table 34](#) by BMI in [Table 35](#), [Table 36](#), [Table 37](#), and [Table 38](#), and by prior receipt of seasonal influenza vaccines in [Table 39](#), [Table 40](#), [Table 41](#), and [Table 42](#). These stratified summaries will be presented for the PP population. It is anticipated that subjects will have little to no pre-existing antibody at baseline, so seroconversion and titer ≥ 40 endpoints will be similar.

8.3.2. Regression Modeling

Logistic and multivariate linear regression will be utilized to test for the effects of the HA antigen dose and the MF59 adjuvant on seroconversion and GMT, respectively, for the PP population. Similar models will be fit for HAI and Neut Antibodies. Separate models will be fit for data from Day 21 post dose 2 and Day 180 post dose 2.

Logistic regression will be fit to examine the relationship of HAI seroconversion at 21 days after the 2nd study vaccination with study arm. If the available titer data meets the required assumptions of normality after log transformation, multiple linear regression will be fit to examine the relationship of log transformed titers at 21 days after the 2nd study vaccination with study arm. Both models will be fit with and without adjustment for the following covariates (*Z*): age category (19-34 years, 35-49 years, 50-64 years), sex (female, male), BMI (<30, ≥ 30), and prior receipt of seasonal influenza vaccine (none in past 2 seasons, at least once in past 2 seasons). Modeling assumptions will be checked using standard diagnostic methods (e.g., using the INFLUENCE option in PROC LOGISTIC or PROC GLM). Parameter estimates and odds ratio estimates for the logistic models will be presented in [Table 43](#), [Table 44](#), [Table 45](#), [Table 46](#), [Table 47](#), [Table 48](#), [Table 49](#), and [Table 50](#). Parameter estimates for the multiple linear regression models will be presented in [Table 51](#), [Table 52](#), [Table 53](#), [Table 54](#), [Table 55](#), [Table 56](#), [Table 57](#), and [Table 58](#).

Model 1A: Logistic Regression (without covariate adjustment):

$$\text{logit}[P(\text{seroconversion})] = \beta_0 + \beta_1 \times \text{Study Arm} + \varepsilon$$

Model 1B: Logistic Regression (with covariate adjustment):

$$\text{logit}[P(\text{seroconversion})] = \beta_0 + \beta_1 \times \text{Study Arm} + \beta_2 \times Z + \varepsilon$$

Model 2A: Multiple Linear Regression (without covariate adjustment):

$$\log(\text{titer}) = \beta_0 + \beta_1 \times \text{Study Arm} + \varepsilon$$

Model 2B: Multiple Linear Regression (with covariate adjustment):

$$\log(\text{titer}) = \beta_0 + \beta_1 \times \text{Study Arm} + \beta_2 \times Z + \varepsilon$$

Subjects missing data for one or more covariates will be excluded from Models 1B and 2B.

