10.5.3 Immunogenicity Data

Summaries and analysis of immunogenicity data will be presented for the mITT and PP populations.

Immune responses in terms of strain-specific 2017 H7N9 HAI and Neut antibody titers will be summarized by treatment arm at each time point. Analyses will include percentage of subjects with a titer ≥ 40 , percentage of subjects achieving seroconversion (defined as either a pre-vaccination titer < 10 and a post-vaccination titer ≥ 40 or a pre-vaccination titer ≥ 10 and a minimum four-fold rise in post-vaccination antibody titer), and GMTs along with corresponding 95% confidence intervals. Descriptive summary statistics will be provided for all assays and time points. The correlation between HAI and Neut antibody titers will be evaluated. Plots such as reverse cumulative distributions or longitudinal presentations of GMTs will be presented.

Additionally, the immune response, as described above, will be summarized by available covariates, such as age, sex, body mass index, and prior receipt of seasonal influenza vaccine(s), and these covariates may be considered statistical modeling. As an exploratory analysis, models will be developed to evaluate the relationship between dosage and adjuvant on immune response. For example, logistic regression may be used to examine the relationship of proportion of responders with dosage and adjuvant, and available covariates may be considered for inclusion in the model.

Additionally, N9 NA specific antibody assays are in development. N9 NA specific responses

may be assessed at baseline, and 8, 22, 29, 43 and 202 after receipt of the first study vaccination. For each time point summaries will include percentage of subjects with detectable N9 NA response (to be defined in SAP following assay development and selection) and GMTs along with corresponding 95% confidence intervals. Descriptive summary statistics will be provided for all assays and time points. The correlation of N9 NA response with HAI and Neut antibody titers will be evaluated, and plots such as reverse cumulative distributions or longitudinal presentations of GMTs will be presented.

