3.2. Endpoints

3.2.1. Primary

Safety:

- Occurrence of study vaccine-related serious adverse events (SAEs) from the time of the first study vaccination through approximately 12 months after the last study vaccination.
- Occurrence of solicited injection site and systemic reactogenicity events from the time of each study vaccination through 7 days after each study vaccination.
- Occurrence of clinical safety laboratory adverse events from the time of each study vaccination through approximately 7 days after each study vaccination.

Immunogenicity:

- For HAI and Neut antibodies, percentage of subjects achieving seroconversion against the influenza 2017 H7N9 study vaccine strain (defined as either a pre-vaccination titer <1:10 and a post-vaccination titer \geq 1:40 or a pre-vaccination titer \geq 1:10 and a minimum four-fold rise in post-vaccination titer) at approximately 21 days after the second study vaccination (Study Day 43).
- For HAI and Neut antibodies, percentage of subjects achieving titer \geq 1:40 against the influenza 2017 H7N9 study vaccine strain at approximately 21 days after the second study vaccination (Study Day 43).
- Geometric Mean Titers (GMTs) of serum HAI and Neut antibodies against the influenza 2017 H7N9 vaccine strain at approximately 21 days after the second study vaccination (Study Day 43).

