6.3.3. Per-Protocol Population

The Per-Protocol (PP) population includes all subjects in the mITT subset with the following exclusions:

- Data from all available visits for subjects found to be ineligible at baseline.
- Data from all visits subsequent to major protocol deviations, such as:
 - Second study vaccination not received,
 - Second study vaccination received out of window,
 - Receipt of non-study licensed live vaccine within 30 days before or after each study vaccination,
 - Receipt of non-study licensed inactivated vaccine within 14 days before or after each study vaccination,
 - Receipt of immunosuppressive therapy (e.g., corticosteroids) within 30 days before or after each study vaccination.
- Data **from** any visit that occurs out of window:
 - Visit 3 data collected before 6 days or after 10 days post first study vaccination
 - Visit 4 data collected before 20 days or after 29 days post first study vaccination.
 - Visit 6 data collected before 6 days or after 10 days post second study vaccination.
 - For subjects who did not receive the second study vaccination, visit 6 data collected before 27 days or after 31 days post first study vaccination.
 - Visit 7 data collected before 20 days or after 29 days post second study vaccination.
 - For subjects who did not receive the second study vaccination, visit 7 data collected before 41 days or after 50 days post first study vaccination.

- Visit 10 data collected before 165 days or after 195 days post second study vaccination.
- For subjects who did not receive the second study vaccination, visit 10 data collected before 200 days or after 216 days post first study vaccination.

For analyses using the PP population, subjects will be grouped based on study vaccinations received.

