8. IMMUNOGENICITY EVALUATION

Analysis of all immune responses will be conducted using the PP population. In addition, primary endpoint analyses will be conducted with the mITT population. Immune responses in terms of strain-specific A/H7N9 HAI and Neut antibody titers will be summarized by study arm at each time point. Descriptive summary statistics will be provided for all assays and time points including number of subjects with non-missing results, percentage of subjects with titers $\geq 1:40$, percentage of subjects achieving seroconversion, and GMTs along with corresponding 95% CI. Exact confidence intervals will be presented for proportional endpoints. Summaries of primary and secondary immunogenicity endpoints are presented in [Table 23](#), [Table 24](#), [Table 25](#), and [Table 26](#).

Reverse cumulative distribution (RCD) curves will be presented for post-vaccination HAI and Neut antibody titers. Plots for each assay will be generated with 4 panels (8 days post vaccination 1, 21 days post vaccination 1, 8 days post vaccination 2, 21 days post vaccination 2, and 180 days post vaccination 2), and separate curves within each panel for each study arm, as shown in [Figure 2](#), [Figure 3](#), [Figure 4](#), and [Figure 5](#).

Figures depicting the HAI and Neut GMT over time will also be presented as shown in [Figure 6](#), [Figure 7](#), [Figure 8](#), and [Figure 9](#).

The spearman correlation between HAI and Neut antibody titers will be calculated at each time point over all groups. The correlation will be depicted in scatter plots as [Figure 10](#) and [Figure 11](#).

Individual HAI and Neut assay results will be provided in [Listing 8](#) and [Listing 9](#).

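### Every planned between-arm immunogenicity model uses the per-protocol set only, so the Day 43 primary endpoints have no as-randomised contrast with a CI or p-value

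*SAP*

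**What the plan says.** **Where the models are restricted to PP.** SAP 8.3.2 tests for effects of antigen dose and adjuvant on "seroconversion and GMT, respectively, for the PP population". Tables 43-58 all carry Per-Protocol in the title. SAP 6.3.3 adds: "For analyses using the PP population, subjects will be grouped based on study vaccinations received". SAP 8.3, the parent section, says: "Immunogenicity data summaries and analysis for exploratory endpoints will be presented for the PP populations". Protocol 10.5.3 gives the models the same status: "As an exploratory analysis, models will be developed to evaluate the relationship between dosage and adjuvant on immune response".

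**Where the text reaches wider.** Protocol 10.5.3 opens with "Summaries and analysis of immunogenicity data will be presented for the mITT and PP populations". SAP 8 first applies PP to all immune responses and then says: "In addition, primary endpoint analyses will be conducted with the mITT population". SAP 8.1, the primary analysis section, states: "Regression modelling of seroconversion and log titers is planned as described in" Section 8.3.2. It names no population of its own. The endpoints being modelled at Day 43 include primary ones: SAP 3.2.1 lists seroconversion and GMTs "of serum HAI and Neut antibodies against the influenza 2017 H7N9 vaccine strain at approximately 21 days after the second study vaccination".

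**What mITT delivers.** SAP 6.3.2 groups mITT subjects by randomised arm. Tables 23 and 25 show GMT, seroconversion and the proportion with titer of at least 1:40 by arm, each with its own interval. No mITT table or figure shows a between-arm difference, ratio, odds ratio or p-value. SAP 12 records no departure from the protocol.

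**The concern.** PP membership at Day 43 depends on what happens after randomisation: receipt and timing of dose 2, other vaccines, immunosuppressive treatment and visit timing. If all contrasts with a CI or p-value rest on that set, the comparison is no longer protected by randomisation. Exclusion could differ by arm. Protocol 8.6.2 withholds dose 2 after a Grade 3 event without alternative etiology in the 8 days after dose 1, and protocol 2.3.1 expects that events may be more frequent in adjuvanted and higher-dose groups. No rate by arm is given.

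Two uses of the contrasts are at stake. Protocol 10.2 notes that a lower confidence limit above zero for the adjuvanted-minus-unadjuvanted difference may be enough to show the adjuvant's added value. The dose-sparing aim in protocol 2.2.1 rests on smaller differences between adjuvanted doses. A reader can subtract the by-arm mITT rates in Tables 23 and 25, but no planned output gives an interval for that difference or a covariate-adjusted version of it.

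**Working it through.** **Inputs from the documents.** Enrolled 106 per adjuvanted arm and 53 unadjuvanted; evaluable 100 and 50; 5% expected exclusion; unadjuvanted response 0.10; adjuvanted response 0.50-0.90; two-sided likelihood ratio test at 0.05 (protocol 10.2); Farrington-Manning limits (SAP Table 7 footnote).

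**Assumptions, not in the documents.** One-dose response r1 of 5-10% in adjuvanted arms; all exclusions are missed second doses; a share f of those subjects has a Day 43 titer, with f from 0 to 1.

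**1. Reproduce the plan's figures.** Farrington-Manning lower limits at 100 versus 50, with 0.10 in the unadjuvanted arm, are 0.256, 0.356, 0.458, 0.563 and 0.672. These match the stated 0.26, 0.36, 0.46, 0.56 and 0.67 in protocol Table 11. Also 106 × 0.95 = 100.7 and 53 × 0.95 = 50.35, in line with 100 and 50.

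**2. Shift within one arm.** With q = 0.05 and two-dose response r2, the PP rate is r2 and

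mITT rate = [(1−q)·r2 + q·f·r1] / [(1−q) + q·f].

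Example: r2 = 0.90, r1 = 0.05, f = 1 gives 0.95 × 0.90 + 0.05 × 0.05 = 0.8575, so PP is higher by 4.25 points.

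| r2, r1 | f=0 | f=0.25 | f=0.5 | f=1 |
|---|---|---|---|---|
| 0.50, 0.10 | 0 | 0.52 | 1.03 | 2.00 |
| 0.50, 0.05 | 0 | 0.58 | 1.15 | 2.25 |
| 0.90, 0.10 | 0 | 1.04 | 2.05 | 4.00 |
| 0.90, 0.05 | 0 | 1.10 | 2.18 | 4.25 |

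(PP minus mITT, percentage points.)

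**3. Other scales, f = 1.** Assume a 2% one-dose response in the unadjuvanted arm, so its mITT rate is 0.95 × 0.10 + 0.05 × 0.02 = 0.096. The odds ratio for 50% versus 10% moves from 9.0 to 8.6-8.7, and for 90% versus 10% from 81 to 57-58. If the two-dose GMT is 4 to 8 times the one-dose GMT (assumed), the PP GMT is higher by a factor of 4^0.05 = 1.07 to 8^0.05 = 1.11.

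**4. Contrast between two adjuvanted doses.** Take PP 60/100 versus 40/100, the 0.20 difference at 40% in protocol Table 10. The statistic is G = 2Σ nᵢ[h(pᵢ) − h(p̄)], where h(p) = p ln p + (1−p) ln(1−p) and p̄ is the pooled rate.
- PP: difference 0.200, G = 8.05, p = 0.0045.
- Add six one-dose subjects per arm (106 − 100), all with Day 43 blood and none responding: 60/106 versus 40/106, difference 0.189, G = 7.62, p = 0.0058. With 10% of them responding (60.6 and 40.6), the difference is again 0.189 and p = 0.0058.

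This contrast needs a difference of coefficients, because the reference arm in Tables 43-58 is 15 mcg unadjuvanted.

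**5. Unequal exclusion (assumed).** Let 10% miss dose 2 in the 60% arm and 2% in the 40% arm, with f = 1 and r1 = 0.05. The mITT rates are 0.90 × 0.60 + 0.10 × 0.05 = 0.545 and 0.98 × 0.40 + 0.02 × 0.05 = 0.393, a difference of 0.152.

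**6. Extreme case for the adjuvant.** Count all 6 and 3 excluded subjects against it: 50/106 versus 8/53. The difference is 0.321 with lower limit 0.172, compared with 0.40 and 0.26 on PP. It stays above zero.

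**The case against.** The case for leaving the plan alone has real force.

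- A reader might infer that the analysis set is unresolved. It is not. SAP 8.3.2 names PP, its parent section limits exploratory endpoints to PP, all 16 table titles agree, and SAP 8.1 defers to 8.3.2. A programmer has one instruction.
- The mITT commitment in SAP 8 can be read as met. The primary endpoints are per-arm percentages and GMTs, and Tables 23 and 25 deliver them on mITT. These tables carry the topline mark; Tables 43-58 do not.
- The protocol calls the models exploratory, and both documents say that no specific null hypothesis is tested. The adjuvant criterion in protocol 10.2 is worded as something that may suffice, so it is not a decision rule.
- A refit may recover few subjects. Nothing is imputed, and those who miss dose 2 are encouraged to give blood about 7 and 21 days after their last dose (protocol 5.2.1), with about 180 days added in the footnotes to SAP Tables 2 and 3. None of these passages asks for Day 43 blood, although SAP 6.3.3 sets a Visit 7 window for such subjects.

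All of this stands, and it limits the point. It does not remove two facts: models of primary endpoints appear under the primary analysis while their parent section treats them as exploratory, and no as-randomised contrast with an interval is planned. PP also drops subjects for an out-of-window dose 2 or Day 43 visit, ineligibility at baseline, or other vaccines. Those subjects may well have Day 43 titers.

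**Conclusion.** The gap is real and modest. It follows from SAP 8.3.2 and the table titles; it is not produced by a conflict between passages. The tension with SAP 8, SAP 8.1 and the opening of protocol 10.5.3 is a separate matter of labelling, left open because SAP 12 declares no change.

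The shift is 0 to 4.3 points in an arm under 5% exclusion, all missed second doses, and a 5-10% one-dose response. A 0.20 dose contrast barely moves under equal exclusion. It moves more only if exclusion differs sharply by arm and the excluded subjects are bled at Day 43, for which the documents give no figures. The adjuvant conclusion holds even in the extreme case.

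A reader might infer that PP restriction could decide whether a dose contrast is significant. The arithmetic bound is 60/106 versus 46/106, difference 0.132, p = 0.054. It requires all six excluded subjects in the better arm to be non-responders and all six in the other arm to be responders with Day 43 titers. That is implausible beside a one-dose response of 5-10%, and nothing in the documents supports it.

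The change is worth making because it is cheap and ends sole reliance on a post-randomisation set. It does not correct a failed confirmatory test.

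**What to change.** 1. Fit the eight Day 43 models (Tables 43, 44, 47, 48, 51, 52, 55 and 56) on mITT by randomised arm as well, using all available Day 43 results, as supportive analyses alongside PP.
2. State in SAP 8.1 and 8.3.2 whether these models are primary or exploratory, and on which set each is fitted.
3. Record in SAP 12 any PP-only restriction that is kept, for example for the Day 180 models.

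The cost is eight more tables from the same model code, a sentence in each of the two sections, and a line in SAP 12. Precision is not lost: if all 106 and 53 were evaluable at the same rates, the lower limits in protocol Table 11 would be 0.26, 0.36, 0.46, 0.57 and 0.68.

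The gain is limited. Subjects without a Day 43 result cannot be restored, those who miss dose 2 are not specifically asked for one, and mITT itself requires a post-dose sample, so it is not a full as-randomised set.

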4.5.2. Immunogenicity Variables

Individual HAI and Neut results will be reported by the central immunology laboratory for the homologous vaccine strain, A/Hong Kong/125/2017 (H7N9), and heterologous strains, A/Shanghai/2/2013 (H7N9) and A/Guangdong/17SF003/2016xPR8/17SF003/2016xPR8 (H7N9). Assay results are reported as a reciprocal titer with values of $10 \cdot 2^k$, where $k=0, 1, 2$, etc. The lower limit of detection for the HAI and Neut assays is 1:10; values below the limit of detection are imputed for analysis as one-half the limit of detection ($10/2 = 5$). For analysis, the geometric mean (calculated on natural log scale) of repeated results for each sample will be computed and used as the response for all subsequent calculations. The variation arising from multiple measurements for an individual at a single time point is not used in subsequent calculations. See Section 3.3 for definitions of derived variables for the analysis of HAI and Neut data.

To assess the Neuraminidase Antigen (NA) specific antibody response to vaccination, it is first necessary to determine the NA content of inactivated influenza vaccine; this assay is under development. If successful, the NA content in a dosage specific manner can be correlated to the N9 NA-specific antibody responses elicited by the 2017 H7N9 IIV. An addendum to the SAP will be generated to outline the planned analyses when assay development is complete.

All immunogenicity data will be uploaded into the SDCC's electronic data capture system.

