5. SAMPLE SIZE CONSIDERATIONS

This study is planned to enroll 106 subjects in each adjuvanted study arm and 53 subjects in the unadjuvanted study arm. Randomization at each site will be stratified by prior receipt of season influenza vaccines, however there is no enrollment target for these strata. The sample size for this study was selected to obtain preliminary estimates in a time critical manner. While this study is not designed to test any specific null hypothesis, the following tables illustrate the precision and power that is available for select estimates and comparisons of interest.

[Table 4](#) indicates the probability of observing one or more safety events, such as solicited injection site or systemic reactogenicity events or an unsolicited non-serious AE of a particular type for a single study arm (N = 53, 106) and for all subjects receiving adjuvanted vaccine (N = 318).

Binomial confidence intervals (CI) are widest (have the least precision) when the response rate is 50%. [Table 5](#) is presented to indicate the worst-case scenario for precision of observed exact (Clopper-Pearson) binomial confidence intervals.

[Table 6](#) illustrates the minimum detectable differences in the proportion of subjects responding (e.g., attaining seroconversion or a titer $\geq 1:40$) between two adjuvanted study arms within each stratum using a two-sided Likelihood Ratio Test and $\alpha = 0.05$.

Power calculations assume $n=100$ per adjuvanted group and $n=50$ for the unadjuvanted group. Based on previous DMID A/H7N9 trials it is expected 5% of enrolled subjects in this stratum may be excluded from analysis of the primary endpoint. In the event that only 100 subjects are actually enrolled in a study arm, the small dropout rates anticipated would have a minimal impact on the calculations presented in [Table 7](#).

Per FDA guidance [5,6], for differences in HAI antibody response rates, the lower confidence limit on the appropriate point estimate excluding equality (i.e., 0 for the difference parameter) may be sufficient to demonstrate the added value of the adjuvant. [Table 7](#) shows the lower bound of the 95% confidence interval for the difference in the proportion of responders between the adjuvanted and unadjuvanted arms (e.g. 15 mcg + MF59 minus 15 mcg unadjuvanted) assuming the proportion of responders in the unadjuvanted arm is 0.10 and considering a range for the proportion of responders in the adjuvanted arm ranges from 0.50 to 0.90.

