15 mcg with MF59 Adjuvant	xxx.x	xxx.x	x.xxx	xx.x	xx.x-xx.x
Age					
19-34 (reference)	-	-	-	-	-
35-49	xxx.x	xxx.x	x.xxx	xx.x	xx.x-xx.x
50-64	xxx.x	xxx.x	x.xxx	xx.x	xx.x-xx.x
Sex					
Female (reference)	-	-	-	-	-
Male	xxx.x	xxx.x	x.xxx	xx.x	xx.x-xx.x
BMI					
<30 (reference)	-	-	-	-	-
≥30	xxx.x	xxx.x	x.xxx	xx.x	xx.x-xx.x
Prior Receipt of Influenza Vaccine					
Did Not Receive 2017-2018 or 2018-2019 Seasonal Influenza Vaccine (reference)	-	-	-	-	-
Received 2017-2018 or 2018-2019 Seasonal Influenza Vaccine	xxx.x	xxx.x	x.xxx	xx.x	xx.x-xx.x

Note: N = Number of subjects with results available at 21 days post second vaccination in the Per-Protocol population. XX subjects missing covariate data were excluded from this analysis.

Tables with similar format:

- Table 48: Logistic Regression Model to Evaluate the Relationship of HA Antigen Dose and MF59 Adjuvant with Neut Seroconversion Against A/Hong Kong/125/2017 (H7N9) at 21 Days Post Second Study Vaccination, Adjusted for Baseline Covariates - Per-Protocol Population**
- Table 49: Logistic Regression Model to Evaluate the Relationship of HA Antigen Dose and MF59 Adjuvant with HAI Seroconversion Against A/Hong Kong/125/2017 (H7N9) at 180 Days Post Second Study Vaccination, Adjusted for Baseline Covariates - Per-Protocol Population**
- Table 50: Logistic Regression Model to Evaluate the Relationship of HA Antigen Dose and MF59 Adjuvant with Neut Seroconversion Against A/Hong Kong/125/2017 (H7N9) at 180 Days Post Second Study Vaccination, Adjusted for Baseline Covariates - Per-Protocol Population**

Table 51: Multiple Linear Regression Model to Evaluate the Relationship of HA Antigen Dose and MF59 Adjuvant with Log-Adjusted HAI Titer at 21 Days Post Second Study Vaccination - Per-Protocol Population

Model Parameter	Parameter Estimate	SE	95%CI	p-value
Intercept	xxx.x	xxx.x	-	x.xxx
Study Arm				
15 mcg without MF59 adjuvant (reference)	-	-	-	-
3.75 mcg with MF59 adjuvant	xxx.x	xxx.x	xx.x-xx.x	x.xxx
7.5 mcg with MF59 adjuvant	xxx.x	xxx.x	xx.x-xx.x	x.xxx
15 mcg with MF59 adjuvant	xxx.x	xxx.x	xx.x-xx.x	x.xxx

Note: N = Number of subjects with results available at 21 days post second vaccination in the Per-Protocol population. XX subjects missing covariate data were excluded from this analysis

Tables with similar format:

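### The log-titer models pool one residual variance over all arms, so their confidence intervals against the unadjuvanted arm are likely to be too wide

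*SAP*

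**What the plan says.** For the titer endpoint, SAP 8.3.2 plans that "multiple linear regression will be fit to examine the relationship of log transformed titers" and study arm. The opening of that sentence makes the linear model conditional: "If the available titer data meets the required assumptions of normality after log transformation, multiple linear regression will be fit". Model 2A regresses log titer on study arm, and Model 2B adds age category, sex, BMI and prior seasonal vaccination. Each is written with one error term. No arm-specific variance, weighting or robust standard error is mentioned. On checking, the SAP says: "Modeling assumptions will be checked using standard diagnostic methods (e.g., using the INFLUENCE option in PROC LOGISTIC or PROC GLM". Equal variance is not named, and no alternative is given if an assumption fails.

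The shells for Tables 51 and 55, whose format the rest of Tables 51-58 follow, label the comparator row "15 mcg without MF59 adjuvant (reference". They print an estimate, SE, 95% CI and p-value for each adjuvanted arm against it.

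Three other places bear on the spread of titers in that arm:

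- SAP 4.5.2: "values below the limit of detection are imputed for analysis as one-half the limit of detection", that is, 5.
- SAP 5, on HAI response rates: "assuming the proportion of responders in the unadjuvanted arm is 0.10". Adjuvanted rates between 0.50 and 0.90 are set against this, with 50 and 100 evaluable subjects per arm.
- SAP 8.3.1 anticipates little or no antibody at baseline.

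**The concern.** A common-variance model is exact only if the arms have the same spread. Here the reference arm is expected to have most subjects below titer 40, many of them recorded at the single value 5, so its log-titer SD should be smaller than in the adjuvanted arms. It also has half the subjects of any other arm. The pooled variance is therefore set mainly by the 300 subjects in the more variable arms and then applied to the 50 in the less variable one. This makes the standard error of every printed contrast too large.

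The protocol (10.1) describes the trial's aim as obtaining meaningful estimates, so interval width is part of what the trial delivers. SAP 8.1 refers the Day 43 titer endpoint to these models, and no other between-arm GMT contrast is planned.

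**Working it through.** **Inputs from the documents.** Evaluable n is 100 per adjuvanted arm and 50 unadjuvanted. P(titer ≥ 40) is 0.10 unadjuvanted and 0.50-0.90 adjuvanted. Titers are 10·2^k, with values below 10 set to 5. The confidence level is 95%.

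**Assumed input.** No log-titer SD is given. Latent log2 titers were taken as normal with SD σ = 1.0, 1.5, 2.0 or 2.5.

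**Check on the plan's own figure.** SAP Table 7 gives lower bounds of 0.26, 0.36, 0.46, 0.56 and 0.67 for the responder difference. Farrington-Manning limits from the same rates and sample sizes are 0.256, 0.356, 0.458, 0.563 and 0.672, which match all five rows. This confirms the rates and sample sizes, not the SDs.

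**Floor share.** Log2(40) and log2(10) differ by 2, and the normal quantile for a 10% upper tail is 1.2816. The share of the unadjuvanted arm recorded as 5 is therefore Φ(1.2816 − 2/σ). This is Φ(−0.72) = 24% at σ = 1.0 and Φ(0.48) = 68% at σ = 2.5.

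**Standard errors of a contrast.** s0 is the SD (natural log) in the unadjuvanted arm, and s1 to s3 are those in the adjuvanted arms.

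- Planned: √[sp²(1/50 + 1/100)], where sp² = [49·s0² + 99(s1² + s2² + s3²)]/346.
- Arm-specific, for adjuvanted arm j: √[s0²/50 + sj²/100].

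**Worked case.** Take σ = 2.0 and adjuvanted rates of 70/80/90%. Then s0 = 0.81 and the adjuvanted SDs are 1.36, 1.38 and 1.39.

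- sp² = [49(0.656) + 99(1.850 + 1.904 + 1.932)]/346 = 1.72. The planned SE is √(1.72 × 0.03) = 0.227.
- For Arm 3 the arm-specific SE is √(0.656/50 + 1.932/100) = 0.180. The ratio is 0.227/0.180 = 1.26.
- On the GMT-ratio scale, the interval is the estimate multiplied and divided by e^(1.96×0.227) = 1.56, against e^(1.96×0.180) = 1.42. Around a ratio of 19.8 this is 12.7 to 30.9, against 13.9 to 28.1.

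**All scenarios.** There were four patterns of adjuvanted rates (50/50/50, 50/60/70, 70/80/90 and 90/90/90%) at each σ, with 20,000 simulated trials per scenario. Width ratio means planned width divided by unequal-variance (Welch) width.

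| σ (log2) | Unadjuvanted arm at titer 5 | s0 | Adjuvanted SDs | Width ratio | Coverage, planned |
|---|---|---|---|---|---|
| 1.0 | 24% | 0.66 | 0.72 | 1.04 | 95.7-96.1% |
| 1.5 | 48% | 0.76 | 1.02-1.06 | 1.15-1.17 | 97.6-98.0% |
| 2.0 | 61% | 0.81 | 1.28-1.39 | 1.23-1.28 | 98.3-98.8% |
| 2.5 | 68% | 0.86 | 1.52-1.72 | 1.27-1.35 | 98.8-99.2% |

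With arm-specific variances, coverage was 94.7-95.3% in all 16 scenarios.

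**Dependence on the SD ratio alone** (equal adjuvanted SDs). Planned SE divided by correct SE is 1.00 at ratio 1.0, 1.15 at 0.75 (coverage 97.6%) and 1.34 at 0.5 (99.1%). If the reference arm were more variable (ratio 1.25), coverage would fall to about 92%, but nothing in the documents points that way.

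**The case against.** The strongest reply is that the model may never be fitted. The pile-up at 5 that compresses the variance also damages normality. In repeated scenarios at the 0.10 rate and σ of 1.25-2.0 (1,000 trials each), Shapiro-Wilk rejected normality of the residuals in 97-100% of trials. The SAP names no normality test, and Shapiro-Wilk is sensitive to discrete titers, so this does not show that the model would be dropped. It does make the point conditional. A normality screen also does not test equal variance.

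A second reply is that assumptions will be checked and INFLUENCE is only an example. That is fair as far as it goes. Equal variance is still not named, however, and the action on failure is left open until after the data are seen.

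Third, the qualitative conclusion would hardly change. Over the same range, the average lower bound of the GMT ratio for Arm 3 against Arm 4 moved only from 2.03 to 2.08 at the small end and from 12.7 to 13.8 at the large end. The smallest pooled t statistic in any trial was 3.5. This stands: the loss is in precision, not in detecting an adjuvant effect.

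Fourth, the models sit under exploratory analyses (SAP 8.3, protocol 10.5.3), and the responder rates are illustrative HAI figures. This also stands. The documents give no such rates for Neut or Day 180, and only Tables 51 and 55 concern HAI at Day 43.

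**Conclusion.** The point holds in a limited form. If Models 2A and 2B are fitted and the unadjuvanted arm sits near the floor as the planning rates imply for HAI at Day 43, the printed intervals are likely to be about 4-35% too wide, with coverage of about 96-99%. The mechanism and direction follow from the documents. The size rests on the assumed SDs, and at σ = 1.0 it is small. If arm SDs prove similar, as they might for Neut or at Day 180, the effect largely disappears.

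A reader might infer more than this, and the documents do not support it:

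- That the intervals are invalid or overstate the adjuvant effect. The error is conservative. No scenario on the planning rates gave coverage below 95%, and Model 2A point estimates do not change.
- That the main GMT results are affected. The intervals in Tables 23-26 are by-arm summaries that do not come from this model. A one-arm interval and a between-arm contrast are different quantities, so a difference between them is not an inconsistency.
- That dose comparisons would be too narrow. Contrasts between adjuvanted arms from the same fit would be slightly so (simulated coverage for Arm 3 against Arm 1 was 93.4-94.8%), but Tables 51-58 do not print them.
- That a still lower unadjuvanted response, and so a larger error, should be expected. The documents give no rate below 0.10.

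**What to change.** In SAP 8.3.2, state that Models 2A and 2B will be fitted with residual variance by study arm (PROC MIXED, REPEATED / GROUP=study arm, Satterthwaite degrees of freedom), or that Tables 51-58 will report HC3 standard errors. HC3 keeps the Model 2B coefficients as they are. Variance by arm reweights the covariate-adjusted fit slightly.

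The cost is one SAP sentence and about one line of SAS code, with no new data. The only downside is slightly fewer degrees of freedom if the variances turn out equal. Fixing it in advance also avoids choosing a variance model after unblinding.
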